10.4.2. Safety Analyses

The safety analysis set will be used in the analysis of safety and data. Data will be listed by subject and summarized. No formal statistical comparisons will be made for safety data.

The number and proportion of subjects with TEAEs will be summarized by treatment, system organ class, and preferred term for all TEAEs, all TEAEs considered by the Investigator to be related to study drug, all SAEs, and all TEAEs leading to study drug discontinuation. All AE summaries will include information for TEAEs that occurred after administration of the first dose of study drug until completion of the final study visit. Data listings will be provided for subjects who discontinued the study due to an AE and for subjects with an SAE.

Selected data will be analyzed using descriptive summary statistics and will be presented by study visit/time point, including the number of non-missing observations, mean and SD, median, upper and lower quartiles, minimum and maximum for values and changes from Baseline. Categorical safety data will be analyzed using frequency tables and, if applicable, shift tables.

Vital signs will be listed by subject and summarized by visit.

Scores from the LTS will be listed by subject and summarized by visit.

10.4.3. Cardiodynamic Assessments

10.4.3.1. Baseline

Time-matched Baseline will be derived from measurements on Day -1 and the morning (pre-dose) of Day 1 for all ECG parameters.

10.4.3.2. By-Time Point Analysis

The QT/QTc analysis set will be used for the by-time point analysis of cardiodynamic ECG parameters. The analysis for QTcF will be based on a linear mixed-effects model with Δ QTcF as the dependent variable, time (i.e., time point: categorical), treatment (tapinarof), and time-by-treatment interaction as fixed effects, and Baseline QTcF as a covariate. An unstructured covariance matrix will be specified for the repeated measures at post-dose time points within subjects. If the model with an unstructured covariance matrix fails to converge, other covariance matrices such as compound symmetry and autoregressive will be considered. From this analysis, the least squares (LS) mean and 2-sided 90% confidence interval (CI) will be calculated at each post-dose time point, separately.

For HR, PR, and QRS intervals, the analysis will be based on the Δ HR, Δ PR, and Δ QRS, respectively. The same (by-time point analysis) model will be used as described for QTcF. The

LS mean, standard error, and 2-sided 90% CI from the statistical modeling for change from Baseline values will be listed in the tables and graphically displayed.

10.4.3.3. Categorical Analysis

10.4.3.4. Concentration-QTc Analysis (Potential Exploratory Analysis)

The PK/QTc analysis set will be used in the potential exploratory concentration-QTc analysis. A potential exploratory concentration-QTc analysis will be performed if a sufficient number of PK samples are above lower limit of quantification to provide a PK profile in most subjects. In this analysis, the relationship between tapinar plasma concentrations and Δ QTcF will be investigated using a linear mixed-effects modeling approach. The following 3 linear models will be considered:

- · Model 1: a linear model with an intercept
- Model 2: a linear model with mean intercept fixed to 0 (with variability)
- Model 3: a linear model with no intercept

Time-matched tapinarof plasma concentration will be included in the model as a covariate, and subject as a random effect for both intercept and slope, when applicable. The model that fits the data best (i.e., has the smallest Akaike information criterion and the model-predicted CIs similar to the observed CIs) will be used for predicting population average $\Delta QTcF$ and its corresponding 2-sided 90% CI at the geometric mean peak tapinarof plasma concentration.

The plot of the observed median-quantile tapinar of plasma concentrations and associated mean $\Delta QTcF$ (90% CI), together with the mean (90%CI) predicted $\Delta QTcF$ (as described by Tornøe, 2011), will be used to evaluate the adequacy of the model fit to the assumption of linearity and the impact on quantifying the concentration-QTc relationship. Additional exploratory analyses (via graphical displays and/or model fitting) will include accounting for a delayed effect (hysteresis) and the justification for the choice of pharmacodynamic model (linear versus nonlinear), as follows.

Investigation of Hysteresis

Hysteresis will be assessed by graphical methods based on the LS mean of $\Delta QTcF$ for each post-dose time point and the mean tapinarof plasma concentrations at the same time points. In addition, hysteresis plots will be given for mean $\Delta QTcF$ and the mean concentrations. If a QT effect ($\Delta QTcF$) > 10 msec cannot be excluded in the by-time point analysis and if a delay between peak plasma levels and peak QT effect ($\Delta QTcF$) in the plot ($\Delta QTcF$ versus tapinarof plasma concentration) of more than 1 hour is present, other concentration-QTc models such as a model with an effect compartment may be explored. With the provision stated above, hysteresis will be assumed if the curve of hysteresis plot shows a counterclockwise loop.

Appropriateness of a Linear Model

To assess the appropriateness of a linear model, normal Q-Q plots for the standardized residuals and the random effects, and plots of standardized residuals versus concentration and versus fitted values will be produced. The scatter plot of standardized residuals versus concentration by LOESS fitting (i.e., locally weighted scatter plot smoothing as described by [Cleveland, 1979]) will also be produced with an optimal smoothing parameter selected by the Akaike information criterion with a correction [Hurvich, 1998]. In addition, a model with the original term and a quadratic term in concentration will be fitted and the quadratic term will be tested on the 2 sided 5% level. If there is an indication that a linear model is inappropriate, additional models will be fitted, in particular an E_{max} model. The concentration-QTc analysis will then be repeated for the model found to best accommodate the nonlinearity detected.

10.4.4. Pharmacokinetic Analysis

The PK analysis set will be used in the analysis of PK data. Data will be listed and summarized. Listings will be sorted by subject, day, and time; summaries will be presented by day and time.

Unless stated otherwise, descriptive summaries for continuous variables will include n, mean, SD, median, minimum, and maximum. If data permit, PK parameters (AUC_{0- τ}, C_{max}, t_{max}, and t_½) will be derived using non-compartmental methods based on the actual sampling times recorded in the study.

10.4.5. Efficacy Analyses

All efficacy analyses will be performed based on the safety analysis set.

PGA Assessments

The PGA will be summarized for the actual, change from Baseline, and percent change from Baseline. The mean and 95% CI for change and percentage change from Baseline will be presented along with p-values based on a one sample t-test.

%BSA Assessments

The %BSA will be summarized for the actual, change from Baseline, and percent change from Baseline. The mean and 95% CI for change and percentage change from Baseline will be presented along with p-values based on a one sample t-test.

PASI Assessments

The PASI will be summarized for the actual, change from Baseline, and percent change from Baseline. The mean and 95% CI for change and percentage change from Baseline will be presented along with p-values based on a one sample t-test.

11. RESPONSIBILITIES

11.1. Investigator Responsibilities

11.1.1. Good Clinical Practice

The Investigator will ensure that this study is conducted in accordance with the principles of the "Declaration of Helsinki" (as amended in Edinburgh, Tokyo, Venice, Hong Kong, and South Africa), International Conference on Harmonization (ICH) guidelines, or with the laws and regulations of the country in which the research is conducted, whichever affords the greater protection to the study subject. For studies conducted under a US Investigational New Drug Application, the Investigator will ensure that the basic principles of "Good Clinical Practice," as outlined in 21 Code of Federal Regulations (CFR) 312, subpart D, "Responsibilities of Sponsors and Investigators," 21 CFR, part 50, 1998, and 21 CFR, part 56, 1998, are adhered to. These standards are consistent with the requirements of the European Community Directive 2001/20/EC.

Since this is a "covered" clinical trial, the Investigator will ensure that 21 CFR, Part 54, 1998, is adhered to; a "covered" clinical trial is any "study of a drug or device in humans submitted in a marketing application or reclassification petition subject to this part that the applicant or US Food and Drug Administration relies on to establish that the product is effective (including studies that show equivalence to an effective product) or that make a significant contribution to the demonstration of safety." This requires that Investigators and all sub-Investigators must provide documentation of their financial interest or arrangements with the Sponsor, or proprietary interests in the drug being studied. This documentation must be provided before participation of the Investigator and any sub-Investigator. The Investigator and sub-Investigator agree to notify the Sponsor of any change of reportable interests during the study and for one year following completion of the study. Study completion is defined as the date that the last subject has completed the protocol-defined activities.

11.1.2. Institutional Review Board/Independent Ethics Committee Approval

This protocol and any accompanying material to be provided to the subject (such as advertisements, subject information sheets, or descriptions of the study used to obtain informed consent) will be submitted by the Investigator to an IRB or IEC. Approval from the IRB or IEC must be obtained before starting the study and should be documented in a letter to the Investigator specifying the protocol number, protocol version, protocol date, documents reviewed, and date on which the committee met and granted the approval.

Any modifications made to the protocol after receipt of IRB or IEC approval must also be submitted to the IRB or IEC for approval before implementation.

11.1.3. Informed Consent/Assent

The Investigator is responsible for obtaining written informed consent/assent from each individual participating in this study after adequate explanation of the aims, methods, objectives, and potential hazards of the study and before undertaking any study-related procedures. The Investigator must utilize an IRB- or IEC-approved consent form for documenting written

informed consent. Each informed consent/assent will be appropriately signed and dated by the subject or the subject's legally authorized representative and the person obtaining consent.

11.1.4. Confidentiality

The Investigator must assure that subjects' anonymity will be strictly maintained and that their identities are protected from unauthorized parties. Only subject number, date of birth, and an identification code (i.e., not names) should be recorded on any form or biological sample submitted to the Sponsor, IRB or IEC, or laboratory. The Investigator must keep a Screening log showing codes, names, and addresses for all subjects screened and for all subjects enrolled in the trial.

The Investigator agrees that all information received from the Sponsor, including but not limited to the investigator's brochure, this protocol, eCRFs, the investigational new drug, and any other study information, remain the sole and exclusive property of the Sponsor during the conduct of the study and thereafter. This information is not to be disclosed to any third party (except employees or agents directly involved in the conduct of the study or as required by law) without prior written consent from the Sponsor. The Investigator further agrees to take all reasonable precautions to prevent the disclosure by any employee or agent of the study site to any third party or otherwise into the public domain.

11.1.5. Study Files and Retention of Records

The Investigator must maintain adequate and accurate records to enable the conduct of the study to be fully documented and the study data to be subsequently verified. These documents should be classified into at least the following two categories: 1) Investigator's study file, and 2) subject clinical source documents.

The Investigator's study file will contain the protocol/amendments, eCRF and query forms, IRB or IEC and governmental approval with correspondence, informed consent, drug records, staff curriculum vitae and authorization forms, and other appropriate documents and correspondence.

The required source data should include at least the following information for each subject:

- Subject identification (name, date of birth, gender);
- Documentation that subject meets eligibility criteria, i.e., history, physical examination, and confirmation of diagnosis (to support inclusion and exclusion criteria);
- Participation in trial (including trial number);
- Trial discussed and date of informed consent;
- Dates of all visits;
- Documentation that protocol-specific procedures were performed;
- Results of efficacy parameters, as required by the protocol;
- Start and end dates (including dose regimen) of study drug (preferably drug dispensing and return should be documented as well);

- Record of all AEs and other safety parameters (start and end date, and preferably including causality and intensity);
- Concomitant medication (including start and end dates, dose if relevant; dose changes should be motivated);
- Date of trial completion and reason for early discontinuation, if applicable.

All clinical study documents must be retained by the Investigator until at least 2 years after the last approval of a marketing application in an ICH region (i.e., US, Europe, or Japan) and until there are no pending or contemplated marketing applications in an ICH region; or, if no application is filed or if the application is not approved for such indication, until 2 years after the investigation is discontinued and regulatory authorities have been notified. Investigators may be required to retain documents longer if required by applicable regulatory requirements, by local regulations, or by an agreement with the Sponsor. The Investigator must notify the Sponsor before destroying any clinical study records.

Should the Investigator wish to assign the study records to another party or move them to another location, the Sponsor must be notified in advance.

If the Investigator cannot guarantee this archiving requirement at the study site for any or all of the documents, special arrangements must be made between the Investigator and the Sponsor to store these in sealed containers outside of the site so that they can be returned sealed to the Investigator in case of a regulatory audit. When source documents are required for the continued care of the subject, appropriate copies should be made for storage outside of the site.

Biological samples at the conclusion of this study may be retained in storage by the Sponsor for a period up to 10 years for purposes of this study.

11.1.6. Electronic Case Report Forms

For each subject enrolled, an eCRF must be completed and signed by the Investigator or sub-Investigator (as appropriate). This also applies to records for those subjects who fail to complete the study. If a subject withdraws from the study, the reason must be noted on the eCRF. If a subject is withdrawn from the study because of a treatment-limiting AE, thorough efforts should be made to clearly document the outcome.

11.1.7. Drug Accountability

The Investigator or designee (i.e., pharmacist) is responsible for ensuring adequate accountability of all used and unused study drug. This includes acknowledgment of receipt of each shipment of study drug (quantity and condition), subject dispensing records, and returned or destroyed study drug. Dispensing records will document quantities received from the Sponsor and quantities dispensed to subjects, including lot number, date dispensed, subject identifier number, and the initials of the person dispensing the study drug.

At study initiation, the monitor will evaluate the site's procedure for study drug disposal/destruction in order to ensure that it complies with the Sponsor requirements. At the end of the study, following final drug inventory reconciliation by the monitor, the study site will dispose of and/or destroy all unused study drug supplies, including empty containers, according to these procedures. If the site cannot meet the Sponsor's requirements for disposal,

arrangements will be made between the site and the Sponsor or its representative for destruction or return of unused study drug supplies.

All study drug supplies and associated documentation will be periodically reviewed and verified by the study monitor over the course of the study.

11.1.8. Inspections

The Investigator should understand that source documents for this trial should be made available to appropriately qualified personnel from the Sponsor or its representatives, to IRBs or IECs, or to regulatory authority or health authority inspectors.

11.1.9. Protocol Compliance

The Investigator is responsible for ensuring the study is conducted in accordance with the procedures and evaluations described in this protocol.

11.2. Sponsor Responsibilities

11.2.1. Protocol Modifications

Protocol modifications, except those intended to reduce immediate risk to study subjects, may be made only by the Sponsor. All protocol modifications must be submitted to the IRB or IEC and regulatory authorities in accordance with local requirements. Approval must be obtained before changes can be implemented.

11.2.2. Study Report and Publications

A clinical study report will be prepared and provided to the regulatory agency(ies). The Sponsor will ensure that the report meets the standards set out in the ICH Guideline for Structure and Content of Clinical Study Reports (ICH E3). Note that an abbreviated report may be prepared in certain cases.

After conclusion of the study and without prior written approval from Dermavant Sciences GmbH, Investigators in this study may communicate, orally present, or publish in scientific journals or other scholarly media only after the following conditions have been met:

- the results of the study in their entirety have been publicly disclosed by or with the consent of Dermavant Sciences GmbH in an abstract, manuscript, or presentation form; OR
- the study has been completed at all study sites for at least 5 years.

No such communication, presentation, or publication will include Dermavant Sciences GmbH confidential information (see Section 11.1.4).

The Investigator will submit any proposed publication or presentation along with the respective scientific journal or presentation forum at least 30 days before submission of the publication or presentation. The Investigator will comply with Dermavant Sciences GmbH request to delete references to its confidential information (other than the study results) in any paper or presentation and agrees to withhold publication or presentation for an additional 60 days in order to obtain patent protection if deemed necessary.

11.2.3. Posting of Information on Publicly Available Clinical Trial Registers

Study information from this protocol will be posted on publicly available clinical trial registers before enrollment of subjects begins. Results will be posted as required.

11.3. Joint Investigator/Sponsor Responsibilities

11.3.1. Access to Information for Monitoring

In accordance with ICH Good Clinical Practice guidelines, the study monitor must have direct access to the Investigator's source documentation in order to verify the data recorded in the eCRFs for consistency.

The monitor is responsible for routine review of the eCRFs at regular intervals throughout the study to verify adherence to the protocol and the completeness, consistency, and accuracy of the data being entered on them. The monitor should have access to any subject records needed to verify the entries on the eCRFs. The Investigator agrees to cooperate with the monitor to ensure that any problems detected in the course of these monitoring visits are resolved.

11.3.2. Access to Information for Auditing or Inspections

To ensure compliance with Good Clinical Practices and all applicable regulatory requirements, Dermavant Sciences GmbH may conduct a quality assurance audit.

Authorized representatives of Dermavant Sciences GmbH, a regulatory authority, an IEC or an IRB may visit the site to perform audits or inspections, including source data verification. The purpose of a Dermavant Sciences GmbH audit or inspection is to systematically and independently examine all study-related activities and documents to determine whether these activities were conducted, and data were recorded, analyzed, and accurately reported according to the protocol, Good Clinical Practice guidelines of the ICH, and any applicable regulatory requirements. The Investigator should contact Dermavant Sciences GmbH immediately if contacted by a regulatory agency about an inspection.

11.3.3. Study Discontinuation

The Sponsor reserves the right to terminate the study at any time. Should this be necessary, the Sponsor will arrange discontinuation procedures and notify the appropriate regulatory authority(ies), IRBs, and IECs. In terminating the study, the Sponsor and the Investigator will assure that adequate consideration is given to the protection of the subjects' interests.

APPENDIX 1. PHYSICIAN GLOBAL ASSESSMENT

Each assessment should be made as a visual 'average' of the severity of all treated areas at the time of the assessment.

Scoring should not be influenced by extent of plaques, participant symptoms, or impact on participant's quality of life.

Score/Grade Description		Description	
0	Clear	No signs of psoriasis; post-inflammatory hyperpigmentation may be present	
1	Almost clear	No thickening; normal to pink coloration; no to minimal focal scaling	
2	Mild	Just detectable to mild thickening; pink to light red coloration; predominantly fine scaling	
3	Moderate	Clearly distinguishable to moderate thickening; dull to bright red, clearly distinguishable erythema; moderate scaling	
4	Severe	Severe thickening with hard edges; bright to deep dark red coloration; severe/coarse scaling covering almost all or all plaques	

APPENDIX 2. CALCULATION OF PERCENT BODY SURFACE AREA AFFECTED AND PSORIASIS AREA AND SEVERITY INDEX

The %BSA affected and PASI will be calculated using the following regional body areas:

- Head and neck
- Trunk, includes internal axillae and groin
- · Upper extremities, includes arms, external axillae, and hands
- Lower extremities, includes legs, buttocks, and feet

Note: At Screening, Baseline and for all efficacy assessments, plaques on scalp, palms, fingernails, toenails, and soles will not be included in the calculation of %BSA affected as these areas will not be included in the efficacy analyses.

Complete the %BSA assessment before the PASI.

Calculation of %BSA Affected:

Measurement of involved BSA is estimated by the handprint method: the total palmar surface of the subject's palm and digits is approximately 1% of their total BSA.

Estimate the involved regional area by determining the number of "full" handprints plus the number of handprints covered if several smaller plaques are "pushed together." Each region can have up to 100% involvement.

- Head and neck = 10% of overall BSA (10 handprints);
 1 hand-sized plaque ~ 10% of head and neck area
- Upper extremities = 20% of overall BSA (20 handprints);
 1 hand-sized plaque ~ 5% of the upper extremities
- Trunk (including axillae and groin) = 30% of overall BSA (30 handprints); 1 hand-sized plaque ~ 3.33% of the trunk
- Lower extremities (including buttocks) = 40% of overall BSA (40 handprints); 1 hand-sized plaque $\sim 2.5\%$ of the lower extremities

Estimates of the % involvement in each body region will be multiplied by the fraction of total body area to obtain the total %BSA involved by region and overall.

Body Region	% Involvement for Each Region (0-100%)	Multiplier	Regional %BSA Involvement
Head and neck		x 0.1	=
Arms / upper extremities		x 0.2	=
Trunk		x 0.3	=
Legs / lower extremities		x 0.4	=
TOTAL Involved	=		

Note: Shaded cells are either fixed values or will be calculated in the eCRF. Multiplier is a fixed number representing fraction of total body area.

Abbreviations: %BSA = percent body surface area.

Calculation of PASI:

After the %BSA involvement for each region is determined, convert each percentage to individual area scores (0 to 6; PASI Item 5) based on the following categories:

	Percentage of skin covered with psoriasis for each of the 4 areas							
Affected	<1%	1 - < 10%	10 - < 30%	30 - < 50%	50 - < 70%	70 - < 90%	≥ 90%	
Score	0	1	2	3	4	5	5	

Using the table below, for Items 1, 2, and 3, generate an average score for erythema, thickness, and scale for each of the 4 body areas using the following 5-point scale:

Item			Body Area					
	Assessment		Head/Neck	Upper extremities (arms)	Trunk (to groin)	Lower extremities (leg to top of buttocks)		
1	Erythema (redness)	(0-4)						
2	Induration (thickness)	(0-4)	90.					
3	Scale (desquamation)	(0-4)						
4	Sum of Items 1, 2, and 3	(0-12)						
5	Area Score	(0-6)						
	Area Multiplier		0.1	0.2	0.3	0.4		
6	Score of (Item 4) x (Item 5) x (Area Multiplier)		Item 4x Item 5x 0.1	Item 4x Item 5x 0.2	Item 4x Item 5x 0.3	Item 4x Item 5x 0.4		
7	Sum of Item 6 for each column is the total PASI score	(0-72)						

Note: Items in shaded rows will be calculated in the eCRF.

Abbreviations: eCRF = electronic case report form; PASI = Psoriasis Area and Severity Index

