4.2. Inclusion Criteria

Each subject must meet all of the following criteria to be eligible to participate in the study:

- 1. Male and female subjects ages 18 to 75 years with confirmed clinical diagnosis of chronic psoriasis and stable disease for at least 6 months prior to the study;
- 2. BSA involvement ≥ 20% (the subject's scalp, palms, and soles should be excluded from the %BSA calculations to determine eligibility at Screening);
- 3. A PGA score of ≥ 3 at Screening;
- 4. WOCBP and male subjects who are engaging in sexual activity that could lead to pregnancy must use at least 1 of the following adequate birth control methods while on study and for 4 weeks after the last exposure to study drug. Acceptable contraception methods are:
 - Male or male partner with vasectomy, OR
 - Male condom AND partner use of one of the contraceptive options below:
 - Spermicide;
 - Contraceptive subdermal implant that meets effectiveness criteria including a < 1% rate of failure per year, as stated in the product label;
 - Intrauterine device or intrauterine system that meets effectiveness criteria including a < 1% rate of failure per year, as stated in the product label;
 - Oral contraceptive, either combined or progestogen alone;
 - Injectable progestogen;
 - Contraceptive vaginal ring;
 - Percutaneous contraceptive patches.

Note: Subjects using hormonal contraceptives must have been on a stable dose for at least 4 weeks before Baseline.

These allowed methods of contraception are only effective when used consistently, correctly, and in accordance with the product label. The Investigator is responsible for ensuring that subjects understand how to properly use these methods of contraception.

Non-childbearing potential is defined as premenarchal; pre-menopausal females with a documented bilateral tubal ligation, bilateral oophorectomy (removal of the ovaries) or hysterectomy; or hysteroscopic sterilization; or postmenopausal females defined as a cessation of menses for at least 12 months without an alternative medical cause. In questionable cases a blood sample with simultaneous follicle-stimulating hormone

(FSH) > 40 mIU/mL is confirmatory. Documented verbal history from the subject is acceptable.

Subjects who are abstinent are eligible, but they must agree to use one of the birth control methods listed above if they start engaging in sexual activity that could lead to pregnancy during the study.

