6.2.3. Psoriasis Area and Severity Index

The PASI scoring system is a widely used standard clinical tool for assessing the severity of psoriasis that takes into account the overall severity of erythema (redness), induration (plaque thickness), and scale, and the extent of %BSA affected with psoriasis. The 3 clinical signs are each graded on a 5-point scale (0 to 4) and the %BSA affected is scored on a 7-point scale (0 to 6) for each of the 4 specified body regions (head, upper extremities, trunk, and lower extremities). The individual scores are multiplied by a weighted factor for each body region; the sum of these scores gives the overall PASI score. Higher scores indicate more severe disease. PASI is a static assessment made without reference to previous scores. Details on PASI calculation are provided in Appendix 2.

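### As read, the PASI area-score row in Protocol Appendix 2 gives 5 to both of its top bands, so the protocol's own 0–6 area score and 0–72 total cannot be reached

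*Protocol*

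**What the plan says.** Protocol 6.2.3 describes the area component of PASI as "scored on a 7-point scale (0 to 6) for each of the 4 specified body regions". Protocol Appendix 2, under Calculation of PASI, repeats that range in the instruction to "convert each percentage to individual area scores (0 to 6; PASI Item 5) based on the following categories". The table below it has seven bands: <1%, 1–<10%, 10–<30%, 30–<50%, 50–<70%, 70–<90% and ≥90%. Its score row reads "Score 0 1 2 3 4 5 5".

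The scoring grid that follows gives Item 4 (severity sum) as 0–12, Item 5 (area score) as 0–6, regional multipliers of 0.1, 0.2, 0.3 and 0.4, and Item 7, described as "Sum of Item 6 for each column is the total PASI score", as 0–72. A footnote adds "Note: Items in shaded rows will be calculated in the eCRF"; the shading cannot be seen in the text, so it is not clear whether the area score is one of those items.

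SAP section 9 analyses change and percent change in PASI from Baseline to Day 29, each with a 95% confidence interval and a one-sample t-test. For the definition it refers back to the protocol appendices. It gives no conversion table of its own, and SAP section 12 (changes to protocol-specified analyses) does not mention PASI.

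**The concern.** Seven bands on a scale running from 0 to 6 need seven different scores. The row as read has only six, because 5 appears twice. The operative scoring table therefore disagrees with four other statements in the same protocol: the lead-in sentence, Item 5, Item 7 and section 6.2.3.

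The table is the rule a programmer would implement, and the SAP points to it. If the row was followed, a region with at least 90% involvement is scored the same as one at 70–<90%. A subject who improves out of the top band loses credit for the reduction in area, and a subject who worsens into it shows no worsening in area. The error is not reliably conservative, so it cannot be set aside on that ground.

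**Working it through.** **Inputs** (Protocol 6.2.3 and Appendix 2): severity sum 0–12 per region; multipliers 0.1 head/neck, 0.2 arms, 0.3 trunk, 0.4 legs (sum 1.0); area score up to 6 as stated, up to 5 as read.

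**Stated maximum.** Maximum PASI = 12 × top area score × 1.0.

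- Top score 6: 12 × 6 × 1.0 = 72, which reproduces Item 7.
- Top score 5: 12 × 5 × 1.0 = 60, which does not.

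**Size for one region at ≥90%.** The relative loss is (6 − 5)/6 = one sixth. The absolute loss is severity sum × multiplier, so at most 12 × multiplier: 1.2 head/neck, 2.4 arms, 3.6 trunk, 4.8 legs, where ≥90% can be reached.

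**Can ≥90% be reached?** Appendix 2 says "Each region can have up to 100% involvement". It also says "plaques on scalp, palms, fingernails, toenails, and soles will not be included in the calculation of %BSA affected", while keeping 10, 20 and 40 handprints as the denominators for head/neck, arms and legs.

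- Trunk: no excluded site, so the top band is open.
- Arms: without two palms (about 2 handprints), at most (20 − 2)/20 = 90%, and marginally less once fingernails are also left out.
- Head/neck: 90% only if the scalp takes no more than 1 handprint, (10 − 1)/10.
- Legs: 90% only if the excluded sites take no more than 4 handprints, (40 − 4)/40.

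The documents do not settle this for the last three regions.

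The entry rule ("BSA involvement ≥ 20", in percent) allows such a region but does not require one. Trunk alone at 90% is 0.9 × 30 = 27% BSA and legs alone at 90% is 0.9 × 40 = 36%, but legs at 50% already give 0.5 × 40 = 20%.

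**Direction.** Let D be the sum, over regions at ≥90%, of multiplier × severity sum, with D0 at Baseline and D1 at Day 29. Let T0 and T1 be the totals with the top band scored 6. The totals as read are T0 − D0 and T1 − D1.

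- Absolute change as read minus change with 6 = D0 − D1. A positive value understates improvement; a negative value overstates it or hides worsening.
- The Day 29/Baseline ratio as read equals T1/T0 × (1 − D1/T1)/(1 − D0/T0). Percent improvement is therefore overstated when D1/T1 exceeds D0/T0, and understated when it is smaller.

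**Hypothetical subjects:**

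| Case | As read | Top band = 6 | D0 − D1 |
|---|---|---|---|
| A. Legs 95% to 75%, severity 9 to 5; other regions area score 2, severity 6 to 3 | 25.2 to 13.6: −11.6 (−46.0%) | 28.8 to 13.6: −15.2 (−52.8%) | 3.6 − 0 = +3.6 |
| B. As A, but legs stay ≥90% | 25.2 to 13.6: −11.6 (−46.0%) | 28.8 to 15.6: −13.2 (−45.8%) | 3.6 − 2.0 = +1.6 |
| C. Legs stay ≥90%, severity 6 to 8; trunk area score 4, severity 9 to 3; other regions clear | 22.8 to 19.6: −3.2 (−14.0%) | 25.2 to 22.8: −2.4 (−9.5%) | 2.4 − 3.2 = −0.8 |
| D. Trunk only, 80% to 92%, severity 6 throughout | 9.0 to 9.0: 0.0 (0%) | 9.0 to 10.8: +1.8 (+20%) | 0 − 1.8 = −1.8 |

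Case A in full: the other regions go from 6 × 2 × 0.6 = 7.2 to 3 × 2 × 0.6 = 3.6. Legs at Baseline are 9 × 5 × 0.4 = 18.0 as read, or 9 × 6 × 0.4 = 21.6 with 6. Legs at Day 29 are 5 × 5 × 0.4 = 10.0 either way.

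A understates improvement on both scales. B understates the absolute change and very slightly overstates the percent change (D1/T1 = 2.0/15.6 = 0.128 against D0/T0 = 3.6/28.8 = 0.125). C overstates improvement. D hides a worsening.

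**Illustration for the mean over 20 subjects.** Assume k subjects all shift the same way, by between −1.8 (case D) and +3.6 (case A). The mean shifts by k × (−1.8 to +3.6)/20: nothing for k = 0, −0.09 to +0.18 for k = 1, −0.45 to +0.90 for k = 5. These are not bounds, and the documents support no particular k.

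**The case against.** The strongest reply is that there may be no error in the plan. Everything turns on one digit in a table read from PDF by a program, and the neighbouring PASI grid contains a stray number that looks like reading noise. A 6 misread as a 5 is quite possible. This stands as a condition on the finding, although the row itself is not visibly broken: seven bands line up with seven scores.

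A second reply is that the slip corrects itself, since four other statements leave only 6 for the top band and a competent programmer would have used it. Nothing available shows that 5 was programmed. This also stands as a condition: if 6 was programmed, no result changes. But the table is the rule the SAP refers to, and nothing in the SAP corrects it. The double programming in SAP Appendix B would not catch the error if both programmers worked from a specification containing 5.

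Third, little depends on it. PASI change is one of three secondary efficacy measures in an open-label, single-arm study with no hypothesis-based sample size, and the safety, PK and QTc endpoints do not use the area score. The excluded sites also make ≥90% doubtful for some regions, arms in particular. These points keep the finding minor. They do not remove it, because the trunk can clearly reach the top band.

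**Conclusion.** The inconsistency holds as stated. As read, the area-score row cannot produce the protocol's own 0–6 area score or 0–72 total; its maximum is 60. If the row was used, each region at ≥90% loses one sixth of its score, and change from Baseline can be understated or overstated on both the absolute and the percent scale.

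The conclusion about results is conditional on three things the documents do not show: that the source page really reads 5, that the eCRF or the derived dataset used 5, and that at least one subject had a region at ≥90% at Baseline or Day 29. The effect on the reported mean therefore cannot be quantified and may be nil. This is a minor point, held with medium confidence.

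**What to change.** 1. Check the last digit of the score row on the source page of Protocol Appendix 2. If it is 6, close the point.
2. If it is 5, state in the SAP that ≥90% scores 6, the only value consistent with 0–6 and 0–72. There is a precedent: SAP Appendix D, section 6.2, already corrects a protocol figure (the QRS outlier threshold) in a footnote.
3. Confirm which score the annotated eCRF (version 1.4, listed in SAP section 2) and the derived-dataset algorithm use. Comparing the planned BSA evaluation listing (16.2.6.2.1) with the derived PASI listing (16.2.6.3.2), for any region at ≥90%, would show it.
4. If 5 was used, recompute PASI and its changes from the regional percentages.

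The cost is a page check, one line in the SAP and a check of the derivation. No new data should be needed, provided the eCRF holds the regional percentages, as the Appendix 2 form and the listing title suggest. Changing the protocol table itself would be a protocol modification, with the submission and approval required by Protocol 11.1.2 and 11.2.1.
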